**Protocol Version 1.13 April 4, 2020**

**1. Background and specific aims:** In the United States (U.S.), Black women are three times more likely to experience iron deficiency (ID) in pregnancy compared to women from other racial/ethnic groups, for reasons that remain largely unknown. Women who are iron deficient during pregnancy experience higher rates of maternal and infant mortality, preterm birth, low infant birth weight, and irreversible neurocognitive defects in their children. Indeed, the highest rates of adverse maternal-infant health outcomes occur in Black women, a phenomenon that may be driven by their sub-optimal iron status. Specific to Chicago, in some low income predominately Black neighborhoods (e.g. Englewood, Austin), preterm birth rates range between 18.5% and 34.8% far exceeding the national average of 9.6% and the state of Illinois at 10.3%. *Exposure to structural violence may compromise maternal iron status that contributes to adverse maternal-infant health outcomes in Black women in at-risk communities.*

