**Specific Aim 1:** To determine the impact of consuming daily Lp299v + standard PNVI vs. standard PNVI + placebo beginning between 15-20 weeks gestation through delivery on maternal iron status and metabolism. To fully characterize maternal iron metabolism and regulators of maternal iron metabolism we will measure several blood-based markers including hemoglobin, hematocrit, ferritin, transferrin receptor, transferrin saturation, serum iron, erythropoietin, systemic inflammation and hepcidin at baseline, 24-28 and 34 - 36 weeks gestation, and at

delivery. *Hypothesis: Women consuming Lp229v will have superior iron status at –24-28 and 34 - 36 weeks gestation and at delivery compared to control women.*

**Specific Aim 2:** To determine colonization and propagation of the gut microbial community with Lp299v from rectal swabs collected at baseline, 24-28 weeks and 34 - 36 weeks gestation in women consuming Lp299v + standard PNVI vs. standard PNVI + placebo. *Hypothesis: Women consuming LP299v will have greater colonization and propagation of Lp299v in their rectal swabs at –24-28 week and 34 - 36 weeks gestation compared to women consuming PNVI + placebo.*

**Specific Aim 3:** To explore the effect of daily oral Lp299v vs. placebo on infant iron status at delivery. Infant iron status will be measured (via cord blood at delivery) (i.e., hemoglobin, ferritin, transferrin, serum iron, and transferrin receptor). *Hypothesis: Infant of women consuming LP299v will have higher iron status at delivery.*

**Specific Aim 4:** To determine the feasibility and tolerability of daily oral Lp299v supplementation (15-20 weeks gestation-delivery). *Hypothesis: Feasibility and tolerability will be high in both treatment groups of the study for the duration of the trial.*

**Exploratory Aim 1:** There is some evidence that probiotic use can positively influence maternal health outcomes including mood. We will explore differences in the development of gestational hypertension, pre-eclampsia, and gestational diabetes using data extracted from the electronic health record (EHR). We will also examine changes to maternal stress response (i.e., serum 17-hydroxycorticosterone and hair cortisol via immunoassay) and self-reported stress, depression, anxiety, resilience, experiences of discrimination, childhood trauma, social support, post-traumatic stress, and spirituality via surveys in women consuming Lp299v + standard PNVI vs. standard PNVI + placebo.

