- a. **Lp299v + standard PNVI.** Starting at 15-20 weeks gestation, women assigned to this group will consume Lp299v + standard PNVI capsules each, once daily, through delivery. Women will be asked to consume both pills with dinner along with a cold or room temperature beverage. The Lp299v supplement will be provided by NatureMade, Pharmavite. This probiotic formulation has a bacterial density of  $10^{10}$  colony forming units (CFUs) per capsule. The PNVI is from NatureMade, Pharmavite and the nutrient content is comparable to a standard prenatal plus vitamin prescribed by clinicians at UIC. The PNVI contains 27 mg of iron as ferrous fumarate. The pills will be provided in separate Pillsy containers and labeled as Vitamin and just generically as “supplement”. Women will receive 30-40 days of pills at the baseline visit and asked to start taking the pills on the 1st day of the 15th-20th gestational week. [name], Associate Professor of Clinical Obstetrics & Gynecology at UIC and Director of the Center for Women’s Health, will write the prescription for both the Lp299v and standard PNVI. The UIC Pharmacy will fill the prescription and deliver to the CRC. Women will pick up new pills at UIC every 28 days during a scheduled standard care prenatal visit or during a separate pill pick up or research data collection visit. If necessary, research staff will hand deliver supplements to the participant home if requested.
- b. **Standard PNVI + placebo.** Starting at 15-20 weeks gestation, women assigned to this group will consume standard PNVI + placebo once daily, through delivery. Taste and packing of the placebo will be identical to the Lp299v, minus the Lp299v, and will be produced by the UIC Pharmacy. Women will be asked to consume both pills with dinner along with a cold or room temperature beverage. The PNVI is from NatureMade, Pharmavite. The PNVI nutrient content is comparable to a standard prenatal plus vitamin prescribed by UIC clinicians. The PNVI contains 27 mg of iron as ferrous fumarate. The pills will be provided in separate Pillsy containers and labeled as Prenatal Vitamin Tablets and Probiotic or Placebo Capsules. Women will receive 30 days of pills at the baseline and asked to start taking the pills on the 1st day of the 15th-20th gestational week. Women will pick up new pills at UIC every 28 days and whenever possible during a scheduled standard

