We will monitor adherence using electronic pill monitoring technology Pillsy and standard pill counts. Women will get a new 30-40-day allotment of pills. During these visits, we will download data from the Pillsy app on their smart phones and conduct a physical pill count. If a woman is found to be non-compliant (i.e., consuming <75% of pills) with her permission, she will receive automated daily text messages around dinner time to help increase compliance with the supplement interventions.

**Pill pick up and adherence monitoring visits (approximately @ 18-19 weeks, 22-23 weeks, 30-31 weeks, 38-39 weeks).** We will monitor adherence using electronic pill monitoring technology Pillsy and standard pill counts. Women will visit UIC approximately every 28 days to get a new 30-40-day allotment of pills and for compliance to be assessed. If possible, these encounters will be coordinated around standard clinical prenatal care appointments. If not, separate pill pick up visits and under certain conditions home pill drop-off will be coordinated. During these visits, we will download data from the Pillsy app on their smart phones and conduct a physical pill count. If a woman is found to be non-compliant (i.e., consuming < 75% of pills) with her permission, she will receive automated daily text messages around dinner time to help increase compliance with the supplement interventions. We will administer the GI symptoms checklist at each visit.

- c. Feasibility and Tolerability. Feasibility will be based on accrual and withdrawal/loss to follow-up rates at the end of the study and adherence determined using the Pillsy smart bottles and standard pill counts. The intervention will be considered feasible if 50% of women approached for participation enroll, overall withdrawal rate is  $\leq 15\%$  and adherence to the supplement regimen is  $\geq 85\%$ . Tolerability [(potential adverse events (AEs) (e.g., GI symptoms)] will be assessed via phone/email/text using the Pillsy app weekly for the first 4 weeks and bi-weekly thereafter. The intervention will be deemed tolerable if no serious AEs (highly unlikely) are documented, and the rate of non-serious AEs is similar between study arms.

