The rectal swabs microbial 16s rRNA sequencing data will be analyzed with QIIME and PICRUSt. Baseline microbial abundance, diversity, and predicted microbial metabolisms will be assessed. For feasibility, # of charts screened, prescreening eligible, approached, and enrolled will be calculated. The # of visits completed at each time point and end of study attrition will be determined and differences between groups calculated. Adherence (# of pills consumed) and # of SAEs/AEs will be calculated and compared between groups. Maternal stress response, maternal iron-related parameters, and inflammation at baseline, 24-28 weeks, 34-36 weeks and labor and delivery, will be evaluated using repeated measures ANOVA and ANCOVA to adjust for baseline differences. Infant iron status at delivery will be compared between groups (Student's t-test). Microbial abundance, diversity and microbial metabolisms will be compared between groups at baseline, 24-28 weeks, 34-36 weeks (Student's t-test/Mann Whitney U) and within group changes at 24-28 weeks and 34-36 weeks will be determined. The mediating effects of maternal rectal swabs microbiome, systemic inflammation and iron regulatory responses on the relationship between Lp299v on maternal stress- and iron-related outcomes will be explored using generalized linear models. Multiple comparisons and false discovery rate adjustments will be used accordingly.

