#### **XIV. Data and safety monitoring plan.**

The PI will establish a data safety monitoring plan and follow all procedures for the protection of human subjects as required by UIC. The purpose of this data and safety monitoring plan is: (1) to ensure the safety of study subjects and the validity of data; and (2) to produce high quality research while considering both risks and benefits. The PI and research assistants will meet weekly to monitor the components of the research study.

Assessment of study risk. The probiotic proposed for use in the study is not contraindicated during pregnancy and therefore has not been shown to pose any adverse risk to the pregnant woman or her fetus. All other study procedures, based on UIC guidelines should be determined as minimal risk.

Data monitoring plan. The PI will monitor the following items: data quality, completeness, and timeliness; adequacy of compliance with goals for recruitment and retention, including those related to participation of minorities; adherence to the protocol; and adverse events reported by subjects at study and adherence visits. If an adverse event is reported during the study, subjects will be requested to report the event to their physician and the PI. All adverse events will be documented and reported to the UIC IRB in a timely manner based on the type of adverse event (adverse event vs. serious adverse event). We will also record and track reasons for dropout. All authorized study personnel will be required to notify the PI of any unanticipated problems/adverse events immediately upon discovery. The PIs will immediately notify the UIC IRB. The study will be subject to annual review and recertification by the OPRS.

Experimental Aim 2: The Maternal Stress Reduction Project, "Happy Moms" Focus Groups  
Information collected from the focus groups will help inform the development of a curriculum focusing on lifestyle and dietary approaches to reduce chronic stress from structural violence. The curriculum will be developed into a series of classes that will be offered at the New Moms Austin Chicago location. The classes will be open to focus group participants and women currently participating in Family Support programs offered by New Moms.

The Maternal Stress Reduction Project, "Happy Moms": Recruitment, Eligibility, Informed Consent and Data Collection

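### The Aim 4 tolerability rule puts no arm, relatedness or comparative limit on serious AEs, so read literally one background event fails it and the planned between-arm comparison goes unused

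*Combined protocol and SAP*

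**What the plan says.** The only tolerability criterion for Specific Aim 4 is in Section 2, VI.c (Feasibility and Tolerability). The intervention is to be "deemed tolerable if no serious AEs (highly unlikely) are documented, and the rate of non-serious AEs is similar between study arms". The first condition is a zero count; the second is a comparison with no measure, margin or interval. The feasibility criteria in the same paragraph are numeric (50% enrolment of women approached, withdrawal at most 15%, adherence at least 85%).

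Section XIII (Statistical analysis) separately plans an arm-level comparison: "Adherence (# of pills consumed) and # of SAEs/AEs will be calculated and compared between groups". It names no test or interval for AEs and does not link the result to the tolerability verdict.

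Section XIV (Data and safety monitoring plan) states: "All adverse events will be documented and reported to the UIC IRB in a timely manner based on the type of adverse event". Events are sorted into serious and non-serious for reporting. The documents give neither a definition of a serious AE nor an assessment of relatedness.

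The Aim 4 hypothesis in Section 1 reads: "Feasibility and tolerability will be high in both treatment groups of the study for the duration of the trial".

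**The concern.** A tolerability conclusion about Lp299v should depend on what happens under Lp299v relative to placebo. The serious-AE condition does not do this: taken as written, it is failed by one event, whichever arm it falls in and whatever its cause. Women are followed through delivery, so some serious events unconnected with the supplement are possible, and the rule cannot tell these from product effects. The trial has a placebo arm and a plan to compare counts between arms, which is the information needed to separate the two, but the verdict makes no use of it.

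At stake is the stated Aim 4 conclusion: a product that adds no risk could be reported as not tolerable. The second condition adds a smaller gap. With no criterion for *similar*, the reader cannot know what difference in non-serious AEs would pass. That gap alone would be missing detail; it matters here because the same sentence has to be rewritten anyway.

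**Working it through.** **Inputs.** Total enrolment is 40 (Section 2, I). The allocation ratio is not stated; 1:1, or 20 per arm, is assumed. The plan gives no serious-AE rate, similarity margin or power figure, so there is no stated result to reproduce. Per-woman probabilities *p* of at least one serious AE from background causes are assumed at 0.5%, 1%, 2% and 5%, equal in both arms (no added risk). Women are treated as independent.

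**Step 1. Chance that a no-added-risk product fails the zero-count condition.** For *n* women counted, P(fail) = 1 − (1 − p)^n.

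| Assumed p | Both arms, n = 40 | Lp299v arm only, n = 20 |
|---|---|---|
| 0.5% | 1 − 0.995^40 = 18% | 1 − 0.995^20 = 10% |
| 1% | 1 − 0.99^40 = 33% | 1 − 0.99^20 = 18% |
| 2% | 1 − 0.98^40 = 55% | 1 − 0.98^20 = 33% |
| 5% | 1 − 0.95^40 = 87% | 1 − 0.95^20 = 64% |

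Failure is as likely as not at p = 1 − 0.5^(1/40) = 1.7% if both arms count, and at p = 1 − 0.5^(1/20) = 3.4% if only Lp299v women count.

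**Step 2. Sensitivity to withdrawal.** At the feasibility ceiling of 15%, 40 × 0.85 = 34 women remain. If only they contributed events, the both-arms figures would be 16%, 29%, 50% and 83%.

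**Step 3. What *similar* could mean.** The plan does not say. Suppose it meant a non-significant two-sided 5% Fisher test (an inference). Exact enumeration over all pairs of counts with 20 per arm gives 19% power for true rates of 20% versus 40%, so that doubling would pass about 81% of the time. Suppose instead it meant lying within a margin *m*, tested one-sided at 2.5% with 80% power and equal true rates *r*. Then n per arm = (1.96 + 0.84)² × 2r(1 − r)/m². With m = 20 points this gives 63 per arm at r = 20% and 83 at r = 30%. Neither a test nor a 20-point margin is workable at 20 per arm.

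**Step 4. What an estimate would look like.** Newcombe 95% CIs for Lp299v minus placebo, 20 per arm: 6/20 versus 6/20 gives −27 to +27 points; 0/20 versus 1/20 gives −24 to +12 points.

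**The case against.** The strongest reply concerns scope. The sentence's subject is the intervention, Aim 4 is about Lp299v supplementation, and the paragraph introduces tolerability with GI symptoms as its example. A reader may therefore take the zero count to mean Lp299v women only. Conversely, a reader may infer that the protocol expressly counts events of any cause in either arm. It does not say that: such breadth follows only from the absence of a qualifier, although the Aim 4 hypothesis does speak of both groups. What can be said is that the scope is unstated. The narrower reading lowers the failure figures, but it still lets an unrelated event decide the verdict.

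A second reply is that a strict zero-event standard for a supplement in pregnancy is a legitimate cautious choice, and that it can coexist with a descriptive comparison. That stands: Sections VI.c and XIII do not contradict each other, and arm-level counts will be available whatever the verdict. The weakness is that the stated conclusion does not use them.

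A reader might also want to take the background event rate from Section 1, which reports that "preterm birth rates range between 18.5% and 34.8% far exceeding the national average of 9.6% and the state of Illinois at 10.3" percent. The documents do not support this. Nowhere do they class preterm birth as a serious AE, and pre-eclampsia appears only as an exploratory outcome. The highest rates belong to some neighborhoods, whereas recruitment is from one health system's clinics, with eligibility limited to singleton, spontaneously conceived pregnancies and with exclusions such as previous premature rupture of membranes, diabetes and tobacco use. Those rates show that obstetric events occur in the wider population; they do not give a serious-AE risk for enrollees.

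Lastly, dropping the verdict leaves Aim 4 without a pass mark for tolerability. That is true, and the hypothesis must be reworded to fit; Step 3 shows why a margin-based replacement is not realistic at this size.

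**Conclusion.** The point holds as a minor one. As written, the serious-AE condition can label a product that adds no risk as not tolerable, in 18% to 87% of trials if both arms count and 10% to 64% if only Lp299v women count, over assumed background risks of 0.5% to 5% per woman. These figures rest on assumed risks, 1:1 allocation and independent women; the documents fix none of these. That the condition is unqualified, and that the planned comparison plays no part in it, rests on the text alone.

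The consequence is limited. For serious AEs the error is in the cautious direction, one conclusion of a 40-woman pilot is affected, no stopping rule in the documents depends on it, and the AE data stay usable. It would go too far to infer that the safety data are compromised or that a true serious-AE excess would be hidden.

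**What to change.** In Section VI.c, replace the zero-serious-AE condition and the word *similar* with a descriptive tolerability assessment built on the comparison already planned in Section XIII. For each arm, report the proportion of women with any serious AE, with any non-serious AE and with each GI checklist symptom. Give the difference (Lp299v minus placebo) with its 95% CI, and make no claim of similarity from a non-significant P value. State the serious-AE definition used for these counts. Align Section XIII, and reword the Aim 4 hypothesis in Section 1 so that it matches what will be reported.

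No new visits, data items or participants are needed: AEs are already documented, and the GI checklist is already given at baseline, follow-up and pill pick-up visits. The cost is wording in three places plus one definition. The downside is that the pre-set yes/no verdict goes and the intervals will be wide, as in Step 4. That width reflects the sample size, and rewording does not cure it.

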**e. Labor and delivery.**

Reminders for contacting research staff and participant tracking. During the 34–36 gestational week research visit and/or at the final pill pick, women will be provided a laminated card with the study number and staff personal contact information. Women will be instructed to contact the research team when they are admitted to UIC labor and delivery. In addition, we will follow the progress of these women closely via phone call, text message, email and through the patient EHR until they are admitted to UIC labor and delivery. UIC labor and delivery staff will also be in-serviced regarding the study procedures.

- 1) Maternal venous blood draw: Following admission, as part of routine care, women will undergo a venous blood collection by labor and delivery staff. As part of this routine care, we will request an additional two tubes of blood (30 ml) for research purposes. If there is extra blood available from the venous blood sample and the patient consents, it may be used for future research to learn more about how to prevent, detect, or treat other health problems in pregnancy.
- 2) Umbilical venous cord blood collection (placental cord blood): Immediately following delivery, the research team will collect a maximum of three tubes of umbilical venous cord blood (~30 mL). If a research participant chooses to bank their umbilical cord blood, and therefore the research team cannot obtain 30 mL of umbilical cord blood, the research team will draw 30 mL of placental blood for analysis. If there is extra cord blood available from the cord blood sample and the patient consents, it may be used for future research to learn more about how to prevent, detect, or treat other health problems in pregnancy.
- 3) Placenta (20 grams): After the cord blood has been obtained, the placenta will be placed in a basin with lid and transferred to the [name] lab space in COMRB. Following placental

characteristics will be examined (i.e., weight, length) and processed for analysis and stored at -80C until later analysis.

- 4) Maternal and infant labor and delivery data: Following participant discharge, a research team member will abstract pertinent maternal and infant L&D data (i.e., route of delivery, infant weight, and infant length) from the EHR.

**VII. Compensation.** Women will receive \$70 at baseline, \$50 at 24-28 and 34-36 weeks and \$29 and gifts of 1 pack each of diapers and wipes at labor and delivery for completing each data collection visit.

Participant incentives for pill pick-ups: Subjects will require supplementation refills 4 times outside of the research visits during the study. Participants will receive 1 pack each of diapers and wipes for each pill pick up. Women completing all aspects of the study will receive up to \$199 dollars.

**VIII. Blood processing and analyses.** All maternal blood samples will be processed at the CON research space and the cord blood samples processed at [name] 3060/3028 COMRB lab space. All samples will be stored at -80°C until analysis. The following assays will be conducted:

1) *Hemoglobin and hematocrit* will be assessed from whole maternal and cord blood in house or at Quest Diagnostics (Chicago, IL).

2) *Serum iron, transferrin saturation, and ferritin* will be quantified from maternal and cord serum at Quest Diagnostics (Chicago, IL).

3) *Soluble transferrin receptor (sTfR)* will be measured from maternal and cord serum via ELISA (R & D systems, Minneapolis, MN).

4) *Hepcidin* will be measured from maternal and cord serum via competitive ELISA at Intrinsic LifeSciences (La Jolla, CA).

5) *Erythropoietin*. Erythropoietin will be measured from maternal and cord serum via ELISA (R & D systems, Minneapolis, MN).

6) *high sensitivity C-Reactive Protein (hs-CRP)* will be measured from maternal and cord serum at Quest Diagnostics (Chicago, IL).

7) *IL-6* will be measured from maternal and cord serum via ELISA (R & D systems, Minneapolis, MN).

8) Circulating stress-related metabolite, serum 17-hydroxycorticosterone will be measured by UIC RRC metabolomics core.

